The PHQ9 will be reviewed by study staff within 24 hours of receiving the questionnaire in the mail. The study staff will score the PHQ9 and a total score >14 (15 and above) and Item 9 is a zero will prompt a review of medical records for current mental health treatment (in consultation or pharmaceutically) of depression. If the patient is not being treated for mental health issues a licensed health care provider will contact the patient and offer a referral or other treatment suggestions. If anything other than “not at all” on Item 9 “Thoughts that you

would be better off dead or of hurting yourself in some way? The participant will be called by a licensed health care provider.

Health Care Utilization: The Study Coordinator will contact all participants at Months 3,6 and 12 via telephone to determine health care utilization, the participants will be asked how many times they have gone to the doctor/Emergency Room/Hospital for breathing problems. In addition, the participants will be asked if they have taken antibiotics or prednisone for breathing related illnesses since the last time the Study Coordinator called them.

Conventional PR group: Referral to Conventional PR (retention strategies)

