Aim 3d: COPD-related hospital readmission (COPD exacerbation or pneumonia as discharge diagnosis) at one month, three months and six months. They will be assessed by the EHR and also by Care Utilization Calls (a safety measure in case individuals are rehospitalized outside the Mayo system). The calls will occur every three months (to avoid recall bias), will use a scripted protocol as in a previous application, and will be conducted by a coordinator blinded to the intervention. Emergency Department (ED) visits and hospitalizations (all cause) will also be recorded.

Aim 4: CE analysis EuroQol Five Dimensions questionnaire

The EuroQol Five Dimensions questionnaire (EQ-5D) is a standardized instrument for measuring generic health status. The health status measured with EQ-5D is used for estimating preference weight for that health status, then, by combining the weight with time, a quality-adjusted life year (QALY) can be computed. QALYs gained its used as an outcome in the cost-utility analysis, which is a type of economic evaluation that compares the benefit and cost of healthcare programs or interventions. EQ-5D is one of the most commonly used generic health status measurements, and its good validity and reliability have been reported in various health conditions. It will be the tool to be used in the proposed cost-effectiveness analysis (CEA).

Secondary Outcomes

Self-Efficacy: The Mastery domain of the CRQ will be used to assess self-efficacy. The CRQ questions assessing self-efficacy are “In the last two weeks, how much of the time did you feel very confident and sure that you could deal with your illness?” and “How often during the last two weeks did you feel you had complete control of your breathing problems?”

Baseline Demographics and comorbidities: Baseline demographics to be collected include age, mMRC, FEV1, highest grade completed in school, marital status, gender, structural and functional social support,³³ race, steroid (prednisone) use in the three months before the study, comorbid conditions (Charlson Comorbidity Index), smoking status, and previous hospitalizations and ED visits.

Analyses

There are three *distinct* quantitative study hypotheses (inform different aspects of the process).

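### The utilization call asks only for a count of breathing-related visits, so it cannot supply the all-cause, dated events that the plan needs from outside the Mayo record

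*Combined protocol and SAP*

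**What the plan says.** The Health Care Utilization paragraph of the Methods sets up the calls: "The Study Coordinator will contact all participants at Months 3,6 and 12 via telephone to determine health care utilization". Participants are "asked how many times they have gone to the doctor/Emergency Room/Hospital for breathing problems". A further question covers antibiotics or prednisone for breathing-related illness since the previous call.

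Aim 3d, among the outcomes of the randomized study, defines the outcome as "COPD-related hospital readmission (COPD exacerbation or pneumonia as discharge diagnosis) at one month, three months and six months". It names two sources, the electronic health record (EHR) and the calls, and describes the calls as "a safety measure in case individuals are rehospitalized outside the Mayo system". It adds that "Emergency Department (ED) visits and hospitalizations (all cause) will also be recorded". The calls are to follow a script and to be "conducted by a coordinator blinded to the intervention". On timing it says: "The calls will occur every three months (to avoid recall bias").

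In the Analyses section, Hypothesis 3d concerns readmissions and ER visits, with no cause named. The later text on healthcare utilization analyses ED visits, hospitalizations and length of stay from baseline to three months, both as yes/no outcomes and as numbers of events, again with no cause named. The secondary endpoint named under Statistical Analysis and Power is COPD-related hospitalization or death.

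**The concern.** For care received outside Mayo, the telephone call is the only source that the plan describes for these outcomes. Its question is narrower than what the plan says it will record and analyse. The resulting variable would be all-cause for events inside Mayo and breathing-related for events outside it, so its meaning would depend on where a patient happened to be treated.

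Two further gaps follow from the wording. A number of visits carries neither dates nor durations. And Aim 3d classifies readmissions by discharge diagnosis, but no section provides for obtaining outside discharge records; the only release described, under Phase 2, is for pulmonary rehabilitation records. Whether an outside admission counts as COPD-related would then depend on whether the patient thinks of it as a breathing problem. The section on the conventional PR group accepts that this kind of intervention cannot be blinded, so that patient knows the assigned arm.

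Information not asked for at the call is hard to recover after follow-up has ended.

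**Working it through.** **1. What each planned quantity needs for an outside event, against what the stated question gives.** For Mayo events the EHR is the source, so this comparison concerns outside events only.

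| Planned quantity | Needed | Given by the question |
|---|---|---|
| All-cause ED visits and hospitalizations (Aim 3d) | Every event, any reason | Breathing-related events only |
| ED visits and hospitalizations to three months, no cause named (Analyses) | Every event, any reason | Breathing-related events only |
| COPD-related readmission at one month (Aim 3d) | Discharge diagnosis and date | Patient's label; no date, and the first call is at month 3 |
| COPD-related readmission at three and six months (Aim 3d) | Discharge diagnosis and period | Patient's label; calls at months 3 and 6 mark the periods |
| Length of stay (Analyses) | Admission and discharge dates | Nothing |

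**2. Share of all-cause admissions missed.** Let *o* be the share of admissions outside Mayo and *r* the share of those that are for non-respiratory reasons. The missed share is *o* × *r*. The documents give neither figure. Assuming *o* from 10% to 40% and *r* from 40% to 60%:

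- low: 0.10 × 0.40 = 0.04, or 4%
- high: 0.40 × 0.60 = 0.24, or 24%

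This range is only as good as its inputs. It concerns all-cause admissions, not the COPD-related endpoint.

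**3. How much loss the powered secondary endpoint could bear.** The plan claims at least 80% power for 50% against 25% at six months with 72 per arm. The 5% two-sided level is stated for the continuous outcomes and is assumed here for this endpoint. Full enumeration of Fisher's exact test gives 84.2%. The pooled normal approximation gives 88.1%: Φ[(0.25 × √72 − 1.96 × √(2 × 0.375 × 0.625)) / √(0.25 + 0.1875)] = Φ(1.18). The claim therefore reproduces.

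Now suppose a fraction *m* of patients with an event goes unrecorded, equally in both arms. The observed rates become 0.50(1 − *m*) and 0.25(1 − *m*):

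| *m* (assumed) | Observed rates | Fisher power |
|---|---|---|
| 0 | 50% vs 25% | 84.2% |
| 5% | 47.5% vs 23.75% | 80.9% |
| 10% | 45% vs 22.5% | 77.4% |
| 20% | 40% vs 20% | 69.7% |

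The margin above 80% is about 4 points and is used up between 5% and 10% loss. This is a sensitivity check, not an estimate. The loss in step 2 does not carry over to *m*: non-respiratory admissions are not part of this endpoint, and a patient with one missed admission may still be counted through another event or through death. Only an outside COPD or pneumonia admission that the patient does not report as a breathing problem would contribute.

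**4. Call months.** Health Care Utilization lists months 3, 6 and 12. Every three months over a year is 3, 6, 9 and 12. The lists differ only at month 9. The Aim 3d windows end at six months, the utilization analysis runs to three months, and the mixed models cover six months. The nine-month summary in the Analyses section is descriptive, with no formal testing.

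**The case against.** The strongest reply is that the named endpoint is COPD-related, all-cause events are an addition to it, and a question about breathing problems suits an endpoint of COPD exacerbation or pneumonia. That is right as far as it goes. A reader might infer that the trial's main utilization outcome is all-cause and is therefore broken; the documents do not support this. What survives is the mismatch with the all-cause recording in Aim 3d and with the analyses that name no cause.

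Second, the call script is not in the documents and may ask more than the Methods paragraph reports. The R33 milestones also provide for collecting adverse-event data, though no method is given. It would therefore be too strong to say that outside all-cause events can never be recorded. The supportable statement is that following the only wording given would miss them; if the script asks more, the paragraph misdescribes it and still needs correcting.

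Third, the caller is blinded, which guards against interviewer influence. It does not govern how the patient labels a visit. A reader might go further and infer bias between arms. For illustration, with true rates of 50% in both arms, losing 10% of events in the home arm alone would raise the Fisher false-positive rate from 3.7% to 7.2%. The home arm does discuss breathlessness with a coach each week, but nothing in the documents shows that labelling would differ by arm, or in which direction. Where patients live is fixed before randomization and should balance on average. One-sided loss is possible but not shown.

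Fourth, a reader might infer from the two call schedules that the three- and six-month results are affected. Both schedules include those months, so they are not.

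**Conclusion.** The concern holds in a limited form. As the question is worded, outside non-respiratory ED visits and admissions would be missed, outside events could not be placed in the one-month window or given a length of stay, and the COPD-related status of outside readmissions would rest on an unblinded patient's label. Mayo events are unaffected by this gap.

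The size is unknown because the share of outside care is not given. The range of 4% to 24% of all-cause admissions follows only from the assumed inputs. For the COPD-related endpoint, an equal loss somewhere between 5% and 10% would take Fisher power below 80%, but the documents do not show that such a loss would occur. The more likely effect is under-counting and a mixed outcome definition, not a demonstrated bias between arms. The repair is cheap enough that it should be made. The difference in call months is a minor inconsistency.

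**What to change.** Reword the utilization question to ask for every ED visit and every overnight hospital stay for any reason, with dates (admission and discharge for stays), facility and reason. Derive the COPD-related subset from the stated reason, or from the discharge diagnosis where the outside record can be obtained. Report outside events classified by self-report separately, or vary their classification in a sensitivity analysis. If calls have already been made with the present wording, record the date of the change.

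State the call months once and use the same list under Health Care Utilization and Aim 3d. If there is no month-9 call, limit the recall-bias justification to the first six months.

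The cost is slightly longer calls, within calls already planned, plus a few added data fields. Obtaining outside discharge records is a further and optional step: it would need a wider release than the one described for pulmonary rehabilitation records, and staff time to request and review the records. Without it, outside events remain classified by self-report, which is why they should be reported separately or tested in a sensitivity analysis.

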Web Universal Resource Locators (URLs), Internet Protocol (IP) address numbers, email address		
Street address, city, county, precinct, zip code, and their equivalent geocodes	x	
Phone or fax numbers	x	
Account, member, certificate or professional license numbers, health beneficiary numbers		

Vehicle identifiers and serial numbers, including license plate numbers		
Check 'None' when none of the identifiers listed above will be recorded, maintained, or shared during the conduct of this study. (exempt category 4)	 None	 None

Data Analysis

Power analyses may not be appropriate if this is a feasibility or pilot study, but end-point analysis plans are always appropriate even if only exploratory. Provide all information requested below, or provide justification if not including all of the information.

Power Statement: The primary endpoint of this study will be the rate of adherence compared between the two groups. Secondary endpoints include rates of COPD related hospitalization or death, activity levels as measured by the average number of steps per day, and the CRQ scales of dyspnea, fatigue, emotional function, physical, mastery, and the total score. Differences between groups will be compared with Fisher’s exact tests for proportions and ttests for continuous endpoints. These analyses will be supplemented with logistic regression models and linear models to compare groups after adjusting for confounding factors.

Data Analysis Plan: One hundred and forty-four patients will be entered on this study (72 per arm). After adjusting for multiple comparisons, this sample size will provide at least 80% power to detect a difference in the rates of adherence of 6% in the control group to 50% in the intervention group. This sample size will also provide at least 80% power for detecting a 50% reduction in hospitalization/death rates (from 50% in the control group at 6 months to 25% in the intervention group at 6 months), a difference of 1000 steps at 3 months (assuming a standard deviation [SD] of 2,000 steps), and a 0.5 difference in CRQ summary scores at 3 months (assuming an SD of 1.0). The sample size will be increased to 150 (75 per arm) to account for a 5% drop out rate.

Statistical Analysis and Power

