The primary endpoint of this study will be the rate of adherence compared between the two groups. Secondary endpoints include rates of COPD related hospitalization or death, activity levels as measured by the average number of steps per day, and the CRQ scales of dyspnea, fatigue, emotional function, physical, mastery, and the total score. Differences between groups will be compared with Fisher’s exact tests for proportions and ttests for continuous endpoints. These analyses will be supplemented with logistic regression models and linear models to compare groups after adjusting for confounding factors.

One hundred and forty-four patients will be entered on this study (72 per arm). After adjusting for multiple comparisons, this sample size will provide at least 80% power to detect a difference in the rates of adherence of 26% in the control group to 50% in the intervention group. This sample size will also provide at least 80% power for detecting a 50% reduction in hospitalization/death rates (from 50% in the control group at 6

months to 25% in the intervention group at 6 months), a difference of 1000 steps at 3 months (assuming a standard deviation [SD] of 2,000 steps), and a 0.5 difference in CRQ summary scores at 3 months (assuming an SD of 1.0). The sample size will be increased to 150 (75 per arm) to account for a 5% drop out rate.

Outcomes for the Phase 2 Randomized study

Aim 3a: Adherence will be our primary outcome

Overview: The reported adherence for PR after a hospitalization is 4% and in the best case scenario (free PR and free transportation like in the UK) is 10%. From our preliminary data, now in press (Respiratory Care), we found an adherence of >80% to the proposed system in outpatients with COPD. We hypothesize the adherence to a complete home-based PR program by post-hospitalized patients will be around 50%, and the adherence to the conventional hospital-based PR program to be 25% (due to our strong efforts to encourage people attend) will consider a complete PR when 75% of the expected PR visits are completed. We will compute the degree of completion of conventional PR from our electronic health record (EHR). The home-based PR compliance will be assessed by the entries of the PR coach in REDCap.

Aim 3b: CRQ Physical and Emotional Summary scores post PR

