Hypothesis 3a (Aim 3a) states that adherence will be higher in subject referred to home PR, will be tested with Fisher’s exact test supplemented with logistic regression adjusting for dyspnea MRC, age, social support, comorbidities, and FEV1. Exploratory analyses will be performed to examine how the number of rehab sessions impacts hospitalization/ED rates, CRQ dyspnea score, CRQ emotional score, and number of daily steps.

Hypothesis 3b (Aim 3b): participants on home-based PR will have higher physical (dyspnea fatigue) and, higher emotional CRQ summary scores at month three than participants who were referred to conventional PR. Tested with t-tests supplemented with linear regression models adjusting for baseline scores and dyspnea MRC, age, social support, comorbidities and FEV1.

Hypothesis 3 c (aim 3c): participants on home-based PR will have more daily PA than participants referred to conventional PR at month three. This will be measured by daily steps and minutes spent in sedentary, light, and moderate activity measured by the ActiGraph.^{30,31} This study has two activity monitors, the ActiGraph, a gold standard activity monitor used for outcome measures (7-day wearing) at baseline, 3, and 6 months; and the Garmin Vivofit PR activity monitor, which will be used daily, but will NOT be used as an outcome measure, rather for PR and health coaching and participant awareness of physical activity (participant will keep this activity monitor). Tested with Wilcoxon tests supplemented with linear regression models adjusting for baseline values and dyspnea MRC, age, social support, comorbidities and FEV1.

Hypothesis 3d (Aim 3d): individuals in the home-based PR program will have lower readmissions and ER visits compared to individual referred to conventional PR. Tested with Fisher’s exact test supplemented with logistic regression models adjusted for hospitalizations in the previous year, age, dyspnea, and comorbidities.

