For the continuous study outcomes, changes from baseline to three months will be compared between the study arms using two-sample, two-sided t-tests with 5% type I error rates. Changes in QOL, number of steps, and length of stay will be compared between the two treatment sequences using two-sample two-sided t-tests. No adjustments will be made for multiple testing. Means, SDs, medians, ranges, and frequency distributions will be reported and plotted over time by study arm. Linear models will be used to assess the impact of treatment arm on three-month outcomes after adjusting for the corresponding baseline measure and other variables related to the outcome (age, degree of breathlessness at baseline using the mMRC dyspnea, and

FEV1). Repeated measures mixed models will be used to estimate the intervention effect over the 6 months of the study (this will measure trajectory and maintenance of benefits / behavior change). Intent-to-treat analyses will also be performed to determine the sensitivity of the results to dropouts and missing values. In the intent-to-treat analyses, if a month three measure is missing for any reason, it will be described as not changing from baseline. Healthcare utilization (number of ED visits, hospitalizations, and length of stay) between baseline and three months will be treated (analyzed) as both binary (for incidence rates) and continuous (for the number of events). The binary endpoints will all be compared between groups using Fisher's exact test. Logistic regression models will also be fit to look for differences in these outcomes by arm after adjusting for age, mMRC, FEV1, baseline levels of anxiety, depression, and fear, and baseline healthcare utilization, (before starting the study) particularly hospitalizations in the previous year.

Descriptive summaries of the changes between baseline, three, six, and nine months will be used to assess the effect of the home based intervention on the control arm and the residual beneficial effect on the intervention arm. These results will be only descriptive and exploratory. No formal hypothesis testing will be done. All data will be stored in REDCap and analyzed using SAS (Cary, NC).

Per-Protocol Analysis (Dose Response): We will conduct an exploratory analysis to assess the effect of dose of PR sessions on study outcomes. This analysis will control for potential confounders of dose.

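### The power statement claims multiplicity-adjusted power that the plan does not provide, and its two copies give control adherence rates of 6% and 26%

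*Combined protocol and SAP*

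**What the plan says.** The same sample-size paragraph stands under Data Analysis Plan and again under Statistical Analysis and Power. Each copy plans 144 patients (72 per arm) and names adherence as the primary endpoint, to be compared with Fisher's exact test.

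- Statistical Analysis and Power: "After adjusting for multiple comparisons, this sample size will provide at least 80% power to detect a difference in the rates of adherence of 26"% for controls, against 50% for home rehabilitation.
- Data Analysis Plan: "a difference in the rates of adherence of 6% in the control group to 50% in the intervention group", under the same claim of adjusted power.
- Outcomes, Aim 3a, hypothesises "the adherence to the conventional hospital-based PR program to be 25"%.
- Both copies also claim 80% power or more for hospitalization/death (50% against 25%), for daily steps (1000, SD 2,000) and for CRQ summary scores (0.5, SD 1.0).
- Analyses: "No adjustments will be made for multiple testing". The only significance level given is for continuous outcomes, "using two-sample, two-sided t-tests with 5% type I error rates".
- Analyses opens with "There are three *distinct* quantitative study hypotheses" and then lists four, 3a to 3d.
- On attrition, both copies say "The sample size will be increased to 150 (75 per arm) to account for a 5% drop out rate".

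**The concern.** The sentence that justifies the sample size claims a property the analysis plan does not deliver. A reader would conclude that 80% power for adherence survives a multiplicity correction. No correction is described, and the Analyses section rules one out. The family of comparisons is also unclear, because three hypotheses are announced and four are listed.

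Separately, two otherwise matching copies give different control rates. One presents the trial as sized for a 44-point contrast (50 − 6), the other for a 24-point contrast (50 − 26). The 6% could pass unnoticed, because Aim 3a cites reported adherence of 4% and 10%. As written, neither the error rate nor the effect behind the design can be read off the document.

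**Working it through.** **Inputs.** From the two sample-size paragraphs: n = 72 per arm; adherence 26% or 6% against 50%; hospitalization/death 50% against 25%; steps 1000/2000 = 0.5 SD; CRQ 0.5/1.0 = 0.5 SD. From Aim 3a: 25%. Two-sided 0.05 is stated for the t-tests and assumed here for Fisher's test.

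**Reproducing the plan's figure.** Exact Fisher power is the sum of Bin(x₁; n, p₁) × Bin(x₂; n, p₂) over all tables whose two-sided Fisher p-value is at most alpha. At alpha 0.05:

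- 26% against 50%: 79.8% at 71 per arm and 80.7% at 72. So 72 is the smallest size that reaches 80%.
- The continuity-corrected formula agrees. Uncorrected, n = [1.960√(2 × 0.38 × 0.62) + 0.842√(0.26 × 0.74 + 0.50 × 0.50)]² / 0.24² = 63.0. Corrected, (63.0/4) × [1 + √(1 + 4/(63.0 × 0.24))]² = 71.1, which rounds up to 72.

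The stated 72 per arm therefore matches 26% against 50% with no adjustment.

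**Other claims, unadjusted, 72 per arm.**

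- Hospitalization/death: 84.2% (Fisher).
- CRQ and steps by t-test: noncentrality 0.5 × √(72/2) = 3.0 on 142 degrees of freedom, giving 84.6%.
- Steps by Wilcoxon: about 83% (simulation, normal data assumed). Hypothesis 3c names this test ("Tested with Wilcoxon tests supplemented with linear regression models adjusting for baseline values"), while the power paragraphs and the later Analyses text name t-tests.

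**If alpha were split equally.** The number of comparisons is assumed, since the plan gives none.

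| Comparisons | Alpha | Adherence, 26% vs 50% | Hospitalization/death | 0.5 SD, t-test |
|---|---|---|---|---|
| 1 | 0.05 | 80.7% | 84.2% | 84.6% |
| 2 | 0.025 | 72.4% | 76.9% | 76.8% |
| 3 | 0.0167 | 66.7% | 71.7% | 71.8% |
| 4 | 0.0125 | 63.4% | 68.4% | 68.1% |

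The lowest two-sided alpha that keeps 80% at 72 per arm is about 0.0435 for adherence, 0.0345 for hospitalization/death and 0.033 for the t-tests.

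**The control rates.**

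- 6% against 50%: 18 per arm suffices (Fisher), and power at 72 per arm exceeds 99.9%. It cannot be the basis of 144.
- 25% against 50%: 84.2% at 72 per arm. The one-point gap between Aim 3a and the 26% is covered.

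**Attrition (minor).** 150 × 0.95 = 142.5, or about 71 per arm, which gives 79.8% for adherence. If dropouts count as non-adherent and all 150 are analysed (75 per arm), power is 83.1% when 26% and 50% are rates among all randomized. If they are rates among those who stay, the contrast becomes 0.95 × 26% = 24.7% against 0.95 × 50% = 47.5%, and power is 79.3%. The R33 milestones count 151 subjects, not 150 (144 × 1.05 = 151.2).

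**The case against.** The best defence is that no computed power figure is wrong. All four claims hold without adjustment. Adherence is the single primary endpoint, so testing it at 5% needs no split, and the equal-split figures describe a procedure nobody proposed. A fixed testing order starting with adherence would keep 80.7% and could fairly be called an adjustment; one-sided 0.025 would also keep 80.7%. The no-adjustment sentence sits in a paragraph that opens with continuous outcomes, whereas adherence is binary. Finally, 6% is probably a dropped digit, and taken literally its power claim is true even after adjustment.

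Much of this stands. The sample size needs no change, and the loss of power is conditional on a method the plan does not name. But the documents state neither a fixed order nor a one-sided test. The no-adjustment sentence is worded without restriction, and its paragraph goes on to cover binary endpoints tested with Fisher's exact test. Even if it applied only to continuous outcomes, the adjustment claimed for adherence would still have no method or alpha and could not be reproduced. That adherence is the only primary endpoint makes the phrase unnecessary; it does not make it correct. The dropped digit is a likely explanation, but the stated design assumption remains wrong in one copy.

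**Conclusion.** The concern holds. The claim of adjusted power has no support in the plan and is contradicted by the Analyses section, and the control rate differs by 20 points between two copies of the same sentence. The size of 72 per arm fits 26% against 50% at an unadjusted two-sided 0.05, with 0.7 points of power to spare. Any equal split of alpha takes adherence to 72.4% or lower. This rests on two-sided 0.05 for Fisher's test, which the plan does not state; the split figures also rest on an assumed number of comparisons. The defect lies in the stated basis of the sample size, not in the number of patients. It should be corrected before analysis, because it concerns the primary endpoint. The 25% in Aim 3a, the attrition rounding and the 151 are minor.

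**What to change.** 1. Delete the multiplicity phrase from both copies of the sample-size paragraph. State that adherence is the single primary endpoint, tested with Fisher's exact test at two-sided 0.05, and that secondary endpoints are tested at nominal 0.05 without adjustment. If an adjustment was really intended, the alternative is to name the method, recompute power and amend the Analyses section.
2. Replace the 6% with the control rate actually used (the arithmetic points to 26%) and use it throughout, including Aim 3a.
3. Restate unadjusted power at 72 per arm: 81% for adherence, 84% for hospitalization/death and 85% for CRQ. For steps, name one test: 85% by t-test or about 83% by Wilcoxon.
4. Make the number of hypotheses agree with the list 3a to 3d.
5. Minor: say either that 5% loss from 150 leaves about 71 per arm (79.8%), or that dropouts count as non-adherent and all 150 enter the primary test (83% or 79%, depending on what the rates refer to). Align 150 with the 151 in the milestones.

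The cost is wording only: no patients are added and the primary test is unchanged. The claim of adjusted power is given up, so secondary results must be reported as unadjusted.
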